### 8.0 DRUG INFORMATION

# 8.1 MEDI4736

8.1.1 Other names Durvalumab

### 8.1.2 Classification - type of agent

MEDI4736, a human IgG1 $\kappa$  mAb directed against PD-L1, contains a triple mutation in the constant domain of the IgG1 heavy chain that reduces binding to C1q and the Fc $\gamma$  receptors

# 8.1.3 Mode of action

MEDI4736 is being developed as a potential anticancer therapy for patients with advanced solid tumors. MEDI4736 is a human monoclonal antibody (MAb) of the immunoglobulin G1 kappa (IgG1 $\kappa$ ) subclass that inhibits binding of programmed cell death ligand 1 (PD-L1) (B7 homolog 1 [B7-H1], cluster of differentiation [CD]274) to programmed cell death 1 (PD-1; CD279) and CD80 (B7-1). MEDI4736 is composed of 2 identical heavy chains and 2 identical light chains, with an overall molecular weight of approximately 149 kDa. MEDI4736 contains a triple mutation in the constant domain of the immunoglobulin (Ig) G1 heavy chain that reduces binding to complement protein C1q and the fragment crystallizable gamma (Fc $\gamma$ ) receptors involved in triggering effector function.

# 8.1.4 Storage and stability

MEDI4736 is formulated at 50 mg/mL in 26 mM histidine/histidine-HCl, 275 mM trehalose dihydrate, 0.02% (w/v) polysorbate 80, pH 6.0.

**Lyophilized formulation:** MEDI4736 is formulated at 50 mg/mL. The investigational product is supplied as a white to off-white lyophilized powder in clear 10R glass vials closed with an elastomeric stopper and a flip-off cap overseal. Each vial contains 200 mg (nominal) of active investigational product. MEDI4736 should be reconstituted with 4.0 mL sterile WFIwater for infusion to give a final concentration of 50 mg/mL. **Liquid formulation:** MEDI4736 is formulated at 50 mg/mL. The investigational product is supplied as a vialed liquid solution in clear 10R glass vials closed with an elastomeric stopper and a flip-off cap overseal. Each vial contains 500 mg (nominal) of active investigational product at a concentration of 50 mg/mL.

Total in-use storage time from needle puncture of MEDI4736 vial to start of administration should not exceed 4 hours at room temperature or 24 hours at 2-8°C (36-46°F). If in-use storage time exceeds these limits, a new dose must be prepared from new vials. Infusion solutions must be allowed to equilibrate to room temperature prior to commencement of administration. MEDI4736 does not contain preservatives and any unused portion must be discarded.

### 8.1.5 Protocol dose specifics

MEDI4736 will be dosed at 750 mg intravenously (IV) every 2 weeks. Patients on Arm 2 will receive MEDI4736 monotherapy and patients on Arm 3 will receive MEDI4736 in combination with tremelimumab.

### 8.1.6 Preparation

MEDI4736 will be supplied in liquid form. Each vial is formulated at 50 mg/mL in 26 mM histidine/histidine-HCl, 275 mM trehalose dihydrate, 0.02% (weight/volume [w/v]) polysorbate 80, pH 6.0. Calculate the dose volume of MEDI4736 and number of vials needed for the subject to achieve the accurate dose.

The preparation of infusion bags should be done under aseptic conditions by trained personnel; it should **not to** be prepared on the floor. The reconstituted solution (for lyophilized product) or liquid product is to be diluted with 0.9% (w/v) saline or 5% (w/v) dextrose for IV infusion.

An additional volume of 0.9% (w/v) saline equal to the calculated volume of MEDI4736 to be added to the IV bag must be removed from the bag prior to addition of MEDI4736. The calculated volume of MEDI4736 is then added to the 250 ml 0.9% (w/v) saline IV bag, and the bag is mixed by gentle inversion to ensure homogeneity of the dose in the bag.

Prior to the start of the infusion, ensure that the bag contents are at room temperature to avoid an infusion reaction due to the administration of the solution at low temperatures. Vials should be used for specific subjects and should not be shared between subjects.

Total in-use storage time from reconstitution of MEDI4736 to start of administration should not exceed 4 hours at room temperature or 24 hours at 2°C to 8°C (36°F to 46°F). If storage time exceeds these limits, a new dose must be prepared from new vials.

### 8.1.7 Route of administration for this study

MEDI4736 will be administered at room temperature (approximately 25°C) by controlled infusion via an infusion pump into a peripheral vein. A central line can be used if needed. Following preparation of MEDI4736, the entire contents of the IV bag should be administered as an IV infusion over approximately 60 minutes ( $\pm$ 5 minutes), using a 0.2- $\mu$ m in-line filter.

The IV line will be flushed with a volume of normal saline equal to the priming volume of the infusion set used after the contents of the IV bag are fully administered, or complete the infusion according to institutional policy to ensure the full dose is administered. Document if the line was not flushed.

### 8.1.8 Incompatibilities

No formal drug-drug interaction studies have been conducted with MEDI4736. There are no known clinically significant interactions of MEDI4736 with other medicinal products. No incomtabilities between MED14736 and polyethylene, polypropylene, polyvinylchloride, or polyolefin copolymers have been observed.

Since the compatibility of MEDI4736 with other IV medications and solutions, other than normal saline (0.9% [w/v][sodium chloride for injection), is not known, the MEDI4736 solution should not be infused through an IV line in which other solutions or medications are being administered.

## 8.1.9 Availability & Supply

The Investigational Products Supply section of AstraZeneca/MedImmune will supply MEDI4736 to the investigator at Northwestern University as a concentrate for solution for infusion.

Investigational products will be supplied by Medimmune in containers with identical appearances in coded kits for each product respectively. Each investigational product kit has a unique number that is printed on all labels within the kit (ie, the outer carton label and the label of each container within the carton). Each carton and vial is labeled with the same unique sequence number range. The investigational product is supplied as a vialed liquid solution in clear 10R glass vials closed with an elastomeric stopper and a flip-off cap overseal. Each vial contains 500 mg (nominal) of active investigational product at a concentration of 50 mg/mL (500 mg/vial).

# 8.1.10 Side effects

Frequent - Expected to occur in 10% to 25% of people (10 to 25 out of 100 people):

• Fatigue (13.5%)

Not Frequent – Expected to occur in 2% to less than 10% of people (2 to less than 10 out of 100 people):

- Nausea (8.4%)
- Diarrhea (5.3%)
- Decreased appetite (5.3%)
- Rash (5.3%)
- Vomiting (4.8%)
- Itchiness (4.1%)
- Difficulty breathing (3.8%)
- Fever (3.1%)
- Low thyroid (2.8%)
- Increased liver enzymes (2.5%)
- Cough (2.5%)
- Muscle pain (2.3%)
- Stomach pain (2.0%)
- Dizziness (2.0%)

### 8.1.11 Nursing implications

Subjects will be monitored during and after the infusion with assessment of vital signs (temperature, pulse, blood pressure and respiratory rate) at the times specified in the Schedule of Assessment (see Section 5.0). On treatment days, vital signs will be measured within an hour prior to start of drug administration, at 30 minutes during the infusion ( $\pm 5$  minutes), at the end of infusion ( $\pm 5$  minutes), and at 30 minutes ( $\pm 5$  minutes) and 60 minutes ( $\pm 5$  minutes) post-infusion. If the infusion takes longer than 60 minutes, then blood pressure and pulse measurements should follow the principles described here or more frequently if clinically indicated. For subsequent doses, the 1-hour observation period will not be required unless a subject experiences an infusion-related reaction.

In the event of a  $\leq$ Grade 2 infusion-related reaction, the infusion rate of study drug may be decreased by 50% or interrupted until resolution of the event (up to 4 hours) and reinitiated at 50% of the initial rate until completion of the infusion.

For subjects with a  $\leq$ Grade 2 infusion-related reaction, subsequent infusions may be administered at 50% of the initial rate. Acetaminophen and/or an antihistamine (e.g., diphenhydramine) or equivalent medications per institutional standard may be administered at the discretion of the investigator. If the infusion-related reaction is  $\geq$  Grade 3 or higher in severity, study drug will be discontinued.

As with any antibody, allergic reactions to dose administration are possible. Appropriate drugs and medical equipment to treat acute anaphylactic reactions must be immediately

available, and study personnel must be trained to recognize and treat anaphylaxis. The study site must have immediate access to emergency resuscitation teams and equipment in addition to the ability to admit subjects to an intensive care unit if necessary.

#### 8.1.12 Return and Retention of Study Drug

Any unused study drug will be destroyed per Northwestern policy.

#### 8.1.13 Accountability and dispensation

Drug supply will be kept in the research pharmacy at Northwestern Memorial Hospital.

#### 8.2 Agent Tremelimumab

8.2.1 Other names

### 8.2.2 Classification - type of agent

Tremelimumab is a human IgG2 anti-CTLA-4 mAb.

#### 8.2.3 Mode of action

Tremelimumab is a human IgG2 mAb directed against CTLA-4. Tremelimumab has an overall molecular weight of approximately 149 kDa including oligosaccharides. Cytotoxic T lymphocyte-associated antigen 4 is a critical regulatory signal for T-cell expansion and activation following an immune response, and it serves as a natural braking mechanism that maintains T-cell homeostasis. During T-cell activation, T cells upregulate CTLA-4, which binds to B7 ligands on antigen-presenting cells, sending an inhibitory signal that limits T-cell activation. Tremelimumab blocks the inhibitory signal resulting from CTLA-4 binding to B7, leading to prolongation and enhancement of T-cell activation and expansion.

### 8.2.4 Storage and stability

Tremelimumab is supplied as a sterile IV solution, filled in 20 mL clear glass vials with a rubber stopper and aluminum seal. Each vial contains 20 mg/mL (with a nominal fill of 20 mL accounting to 400 mg/vial) of Tremelimumab, in an isotonic solution at pH 5.5.

Tremelimumab should be stored at refrigerated temperatures (2°C to 8°C), and should not be frozen. The 20 mg/mL solution will be diluted into a saline bag for IV infusion. Vials containing Tremelimumab may be gently inverted for mixing, but should not be shaken. Total in-use storage time from needle puncture of the product vial to start of administration should not exceed 4 hours at room temperature or 24 hours at 2°C to 8°C (36°F to 46°F). If in-use storage time exceeds these limits, a new dose must be prepared from new vials. Tremelimumab does not contain preservatives and any unused portion must be discarded.

### 8.2.5 Protocol dose specifics

Tremelimumab will be given at a dose of 75 mg IV every 4 weeks. Patients on Arm 1 will receive tremelimumab monotherapy and patients on Arm 3 will receive tremelimumab in combination with MEDI4736.

### 8.2.6 Preparation

Tremelimumab Drug Product is formulated at a nominal concentration of 20 mg/mL in 20 mM histidine/histidine hydrochloride, 222 mM trehalose dihydrate, 0.02% (weight/volume [w/v]) polysorbate 80, 0.27 mM disodium edetate dihydrate (EDTA), pH 5.5.

The Drug Product is supplied as a sterile IV solution in 20 mL clear glass vials with a rubber stopper and aluminum seal. Each vial contains 20 mg/mL of tremelimumab with a nominal fill of 20 mL (accounting to 400 mg/vial). Vials containing tremelimumab must be stored at  $2^{\circ}$  C to  $8^{\circ}$ C ( $36^{\circ}$ F to  $46^{\circ}$ F) and must not be frozen. Vials containing

tremelimumab may be gently inverted for mixing, but should not be shaken.

The product should be protected from light when not in use. Tremelimumab does not contain preservatives and any unused portion must be discarded. Preparation of tremelimumab and preparation of the IV bag are to be performed aseptically. Total in-use storage time from needle puncture of the investigational product vial to start of administration should not exceed 4 hours at room temperature or 24 hours at 2°C to 8°C (36°F to 46°F). It is recommended that the prepared final IV bag be stored in the dark at 2°C to 8°C until needed. If storage time exceeds these limits, a new dose must be prepared from new vials. The refrigerated infusion solutions in the prepared final IV bag should be equilibrated at room temperature for about 2 hours prior to administration.

For dose preparation steps, the following ancillary items are required:

- IV infusion bags of 0.9% (w/v) sodium chloride injection (250 mL size).
- Saline bags must be latex-free and can be made of polyvinyl chloride (PVC)
- or polyolefins (eg, polyethylene), manufactured with DEHP or DEHP-free. IV infusion lines made of PVC/DEHP or PVC/tri octyl trimellitate or polyethylene or polyurethane. All DEHP-containing or DEHP-free lines are acceptable. Lines should contain a 0.22 or 0.2 μm in-line filter. The in-line filter can be made of polyethersulfone or polyvinylidene fluoride. Lines containing cellulose-based filters should not be used with tremelimumab.
- Catheters/infusion sets made of polyurethane or fluoropolymer with silicone and stainless steel and/or PVC components.
- Syringes made of polypropylene and latex-free. Polycarbonate syringes should not be used with tremelimumab.
- Needles made of stainless steel.

### 8.2.7 Route of administration for this study

Tremelimumab is to be administered as an IV solution at a rate of 250 mL/hr., followed by observation for 60 minutes.

For the combination arm, tremelimumab will be administered first. MEDI4736 infusion will start approximately 1 hour after the end of the tremelimumab infusion for the first infusion only. If there are no clinically significant concerns after the first cycle, the MEDI4736 infusion may be administered immediately after the tremelimumab infusion has finished in all other cycles, at the discretion of the investigator. The duration of each infusion will be approximately 1 hour.

### 8.2.8 Incompatibilities

No formal drug-drug interaction studies have been conducted with tremelimumab. However, in RCC studies, acute renal failure has been reported with the combination of tremelimumab and sunitinib. It is unknown whether a similar reaction will be observed when tremelimumab is combined with other tyrosine kinase inhibitors.

# 8.2.9 Availability & Supply

Investigational products will be supplied by Medimmune in containers with identical appearances in coded kits for each product respectively. Each investigational product kit has a unique number that is printed on all labels within the kit (ie, the outer carton label and the label of each container within the carton). Each carton and vial is labeled with the same unique sequence number range.

Tremelimumab is formulated at 20 mg/mL in 20 mM histidine/histidine-HCl, 222 mM trehalose dihydrate, 0.02% (w/v) polysorbate 80, and 0.27 mM disodium edetate dihydrate, pH 5.5. The investigational product is supplied as a clear to opalescent,

colorless to yellowish liquid in a 20-mL clear, glass vial with a rubber stopper aluminum seal. Each vial contains 400 mg (nominal) of active investigational agent. The standard supply of tremelimumab is delivered in a white carton with 16 vials of tremelimumab within foam inserts.

Tremelimumab will be provided to Northwestern University by MedImmune. Northwestern University will request tremelimumab submitted via email. Please allow approximately 10 days for drug delivery.

#### 8.2.10 Side effects

Below are safety data from 973 subjects with various types of cancer who received tremelimumab alone. Related side effects reported in subjects receiving tremelimumab alone were:

# Very Frequent – Expected to occur in more than 25% of people (more than 25 out of 100 people):

- Diarrhea (41.2%)
- Itching (25.1%)

Frequent - Expected to occur in 10% to 25% of people (10 to 25 out of 100 people):

- Fatigue (23.8%)
- Nausea (21.9%)
- Vomiting (13.5%)
- Decreased appetite (11.3%)

# Not Frequent – Expected to occur in more than 5% to less than 10% of people (more than 5 to less than 10 out of 100 people):

- Headache (7.2%)
- Fever (7.0%)
- Stomach pain (6.7%)
- Inflammation of the large intestine (5.5%)

Subjects will be monitored during and after the infusion with assessment of vital signs at the times specified in the Schedule of Assessment (see Section 6.2) On treatment days, vital signs will be measured within an hour prior to start of drug administration, at 30 minutes during the infusion ( $\pm$  5 minutes), at the end of infusion (+ 5 minutes), and at 30 minutes ( $\pm$  5 minutes) and 60 minutes ( $\pm$  5 minutes) post-infusion. If the infusion takes longer than 60 minutes, then blood pressure and pulse measurements should follow the principles described here or more frequently if clinically indicated. For subsequent doses, the 1-hour observation period will not be required unless a subject experiences an infusion-related reaction

In the event of a  $\leq$ Grade 2 infusion-related reaction, the infusion rate of study drug may be decreased by 50% or interrupted until resolution of the event (up to 4 hours) and reinitiated at 50% of the initial rate until completion of the infusion.

For subjects with a  $\leq$ Grade 2 infusion-related reaction, subsequent infusions may be administered at 50% of the initial rate. Acetaminophen and/or an antihistamine (e.g., diphenhydramine) or equivalent medications per institutional standard may be administered at the discretion of the investigator. If the infusion-related reaction is  $\geq$ Grade 3 or higher in severity, study drug will be discontinued.

As with any antibody, allergic reactions to dose administration are possible. Appropriate drugs and medical equipment to treat acute anaphylactic reactions must be immediately available, and study personnel must be trained to recognize and treat anaphylaxis. The study site must have immediate access to emergency resuscitation teams and equipment in addition to the ability to admit subjects to an intensive care unit if necessary.

## 8.2.12 Return and Retention of Study Drug

Any unused study drug will be destroyed per Northwestern policy.

#### **8.2.13** Accountability and dispensation Drug will be kept in the research pharmacy at Northwestern Memorial Hospital.

### 9.0 CORRELATIVES/SPECIAL STUDIES

#### 9.1 Tumor and peripheral lymphocyte changes

Samples will be collected and sent to the laboratory of: [name] [name] Lab [contact] Office [contact] [name] Tissue and blood samples from the operating room and from clinic will be collected by laboratory personnel and sent to the laboratory of [name] in [name] for processing.

**Fresh Tumor tissue**: removed at surgery will be used to extract tumor-infiltrating lymphocytes (TIL) for analysis. In addition, fresh frozen and formalin fixed paraffin embedded tissue will be banked for analysis. Extracted TILs will be used to evaluate the tumor infiltrative lymphocyte population by flow cytometry and paraffin embedded tissue will be used to evaluate TILs in situ by immunohistochemistry. If a patient has progression of disease and undergoes further surgery, they will have the option of allowing tissue to be analyzed for the above.

**Blood sample**: 10ml blood in one 10ml Sodium heparin tube. This will be collected at 1st preoperative treatment, day of surgery, C1D1, and at each adjuvant treatment imaging visits (i.e. every 2 cycles or 8 weeks).

Blood collected prior to treatment on 1st pre-operative treatment day will be used for baseline evaluation of activated peripheral lymphocytes. Patients will then have blood drawn on day of surgery, and on the day of each MRI scan (i.e. every 2 cycles or 8 weeks) with extraction and banking of peripheral blood leukocytes (PBL).

PBLs obtained prior to drug administration will be studied by flow cytometry to identify relative populations of CD8 T cells (CD3+, CD8+, PD1+/-), CD4 T cells (CD3+, CD8+, PD1+/-), regulatory T cells (CD4+, CD25+, FoxP3+), and suppressive monocytes (CD45+, CD11b+, PD-L1+). Repeat assessment of PBL markers will be determined by flow cytometry of subsequent samples taken on the day of surgery, post operatively (C1D1) and then on MRI days. Additionally, TILs extracted from patient tissue will be evaluated for relative populations of activated CD8 T cells (CD3+, CD8+, IFN-g+, PD1+/-), activated CD4 T cells (CD3+, CD8+, IFN-g+, PD1+/-), regulatory T cells (CD4+, CD25+, FoxP3+), and suppressive monocytes (CD45+, CD11b+, CD163+, PD-L1+). CTLA-4 expression on effector and regulatory T cells can also be measured by flow cytometry. Double-labeled tissue immunofluorescence can also be performed on FFPE sections to obtain immune effector cell counts, reported as # cells / 10 hpf. Optimized labeling schemes include: CD8/IFN-g, CD4/IFN-g, CD8/PD-1, CD4/PD-1, CD68/PD-L1, GFAP/PD-L1 (to identify PD-L1+ tumor cells).

We will use our stimulation protocol for IFN-g from PBL to look for increased peripheral T cell reactivity before and after drug treatment

Banked PBLs, TILs and FFPE tissue from prior patients treated without the study drug will serve as comparative controls.

*NOTE:* Any leftover tissue from the study patients will be banked for future use. This should be clearly stated in the consent form.

Please refer to laboratory manual for further details on collection, labeling, shipping, processing and storage.

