# 6.0 ENDPOINT ASSESSMENT

## 6.1 **Primary Endpoint**

To determine the T-cell changes (immunologic changes) that occur in recurrent GBM treated with Tremelimumab and MEDI4736 as single agents and in combination. The changes from baseline will be assessed in blood samples and tissue samples before treatment and post-surgery for all patients in the 3 arms. A comparison between the changes observed in the 3 arms will be made.

Only patients who have had pre-treatment blood sampling, have undergone surgery with pre-surgical blood sampling, and are able to continue to post-operative drug treatment with blood sampling prior to the first post-surgical dose will be evaluable for this endpoint.

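### Section 9.1 gives CD4 T cells the CD8 marker set in both blood and tumour, contradicting its own use of CD4 elsewhere; as written, the CD4 flow readout would duplicate the CD8 readout

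*Combined protocol and SAP*

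**What the plan says.** Section 9.1 lists four populations to be measured by flow cytometry in peripheral blood lymphocytes, and four in lymphocytes extracted from tumour.

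- In blood, the CD8 entry reads "CD8 T cells (CD3+, CD8+, PD1" positive or negative. The CD4 entry reads "CD4 T cells (CD3+, CD8+, PD1" positive or negative.
- In tumour, the CD8 entry reads "activated CD8 T cells (CD3+, CD8+, IFN-g+, PD1" positive or negative. The CD4 entry reads "activated CD4 T cells (CD3+, CD8+, IFN-g+, PD1" positive or negative.
- In both compartments the third population is "regulatory T cells (CD4+, CD25+, FoxP3" positive, and the fourth is suppressive monocytes.

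The same paragraph then describes double-label immunofluorescence on paraffin sections as something that may be done in addition: "Optimized labeling schemes include: CD8/IFN-g, CD4/IFN-g, CD8/PD-1, CD4/PD-1", followed by the PD-L1 pairs.

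Section 6.1 states the primary endpoint as "To determine the T-cell changes (immunologic changes) that occur in recurrent GBM treated with Tremelimumab and MEDI4736 as single agents and in combination", and adds that "The changes from baseline will be assessed in blood samples and tissue samples before treatment and post-surgery for all patients in the 3 arms". Section 2.1 says the same in substance. Neither section names a subset or a marker, and Section 10.3 refers only to immunologic measures and to changes of T cells. Section 9.1 closes by referring to a laboratory manual for specimen handling. That manual is not part of the documents.

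**The concern.** A CD4 T cell cannot be identified by the markers CD3+ and CD8+ that the same text uses to identify a CD8 T cell. The slip sits in the assay section that a laboratory or an analyst would follow, so it is more than loose background wording.

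If it were followed, a result labelled CD4 would report CD8 cells. Any agreement between the CD4 and CD8 results would then be built in by definition. The result would carry through the blood series (pre-treatment, day of surgery, first adjuvant dose, imaging visits), the comparison of arms, the comparison with banked samples from patients not given study drug, and the Cox regression of T-cell changes on survival in Section 10.3. A reader of the final report would have no way to see this from the label.

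**Working it through.** No figure in the plan depends on this point, so the check is a comparison of definitions, all taken from Section 9.1.

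| Where measured | Label in the plan | Markers in the plan |
|---|---|---|
| Blood, flow | CD8 T cells | CD3+, CD8+, PD1+/- |
| Blood, flow | CD4 T cells | CD3+, CD8+, PD1+/- |
| Tumour, flow | activated CD8 T cells | CD3+, CD8+, IFN-g+, PD1+/- |
| Tumour, flow | activated CD4 T cells | CD3+, CD8+, IFN-g+, PD1+/- |
| Both, flow | regulatory T cells | CD4+, CD25+, FoxP3+ |
| Paraffin sections, optional | CD8 and CD4 pairs | CD8 with IFN-g or PD-1; CD4 with IFN-g or PD-1 |

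1. **Blood.** The CD4 marker set equals the CD8 marker set, element for element. The four labels therefore carry three distinct definitions.
2. **Tumour.** The same holds: four labels, three distinct definitions.
3. **Could it be a text-extraction fault?** Unlikely. The two lists are worded differently (the tumour list adds activation and IFN-g), and the same substitution appears in both. Nothing is blacked out there.
4. **Does the document show what was meant?** Yes. The label says CD4. Regulatory T cells are identified by CD4+, and the immunofluorescence labels list CD4 pairs apart from CD8 pairs. Section 1.2 also speaks of peripheral CD4+ and CD8+ T cells as separate populations.
5. **Does another section supply a correct flow definition?** No. No other section defines a conventional or effector CD4 T cell by flow.
6. **Does it touch the sample size?** No. Section 10.3 states 80% power for a difference of 1.25 standard deviations with 10 per group, two-sided 5%. By the normal approximation, power = Φ(1.25 × √(10/2) − 1.96) = Φ(2.795 − 1.960) = Φ(0.835) = 0.798, which reproduces the stated figure (a two-sample t-test calculation gives 0.753). The calculation is in standard-deviation units and uses no marker definition, so correcting the markers leaves it as it is.

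**The case against.** The strongest reply is that this is an obvious misprint. The population is called CD4, the paragraph uses CD4 properly elsewhere, and a flow laboratory would hardly report CD8+ cells under a CD4 label. That is probably right, and it is why the point is an inconsistency to correct and not a design decision to dispute. It does not remove the need for correction. Section 11.6 requires the study to be run as the approved protocol describes, and the laboratory manual, which might settle the matter, is cited only for handling of specimens and cannot be seen here.

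Four stronger readings are tempting, and the documents do not support them.

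- **That no CD4 response would be measured at all.** Regulatory T cells are identified by CD4+, and CD4 immunofluorescence on tissue is available. What is lost is narrower: conventional or effector CD4 cells by flow. The immunofluorescence is optional and limited to tissue, so it cannot stand in for the blood series.
- **That a CD4/CD8 ratio would be spoiled.** With identical definitions such a ratio would be 1 by construction, but no section plans one. The only cell ratio mentioned, CD8+ effector to FoxP3+ regulatory cells in the background of Section 1.2, does not use the faulty definition.
- **That the primary endpoint is itself misdefined.** Sections 2.1 and 6.1 name no subset, Section 9.1 sits under correlative studies, and Section 1.5.1 lists blood and tumour lymphocyte profiling among additional exploratory work. The link is an inference, though a reasonable one, since 9.1 is the only place that says what the T-cell measures are.
- **That the laboratory has in fact counted CD8 cells twice.** The documents cannot show what was done in practice.

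**Conclusion.** The inconsistency is real and appears twice. As written, two of the four flow populations in each compartment share one definition, and the conventional or effector CD4 readout would add no information to the CD8 readout. The regulatory T-cell, monocyte and optional immunofluorescence measures stand.

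The reach to the primary endpoint, and to the correlation of T-cell changes with outcome, rests on one assumption: that the T-cell changes in Sections 2.1, 6.1 and 10.3 are those listed in 9.1. The practical effect rests on a second, that the laboratory follows the printed markers over the label, which cannot be checked from the documents. If the laboratory already uses CD4, the effect is confined to the text. In either case the protocol should be corrected before any CD4 result is reported from it.

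**What to change.** In Section 9.1, replace CD8+ with CD4+ in the two CD4 entries, so that they read:

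- blood, CD4 T cells: CD3+, CD4+, PD1+/-
- tumour, activated CD4 T cells: CD3+, CD4+, IFN-g+, PD1+/-

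Then obtain written confirmation from the laboratory that its manual and analysis settings use these definitions, for samples already analysed and for the banked comparison samples as well as for future ones. If any were analysed as printed, re-analyse the stored cytometry data where CD4 was stained alongside the other markers, and record which samples could not be recovered. The regulatory T-cell definition already calls for a CD4 stain, so the reagent is in use; the documents do not say whether it is in the same tube.

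The cost is two marker changes in the protocol and one query to the laboratory. No new sample or assay is needed for the text correction, and no sample size, power or safety rule changes.
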